6.3.3 Longer term outcomes

Longer term exploratory analyses will be conducted on the HIT, SF-36 and ABNAS (see below) to assess their suitability as outcome measures in future studies of viral meningitis. The SF-36 and ABNAS will be compared with published normative data. [name] from the Walton Centre, who is an expert on validation and implementation of rating scores will provide advice on evaluation of the different scores.

Patients will also be asked to document if they have had any episodes of genital lesions throughout the follow-up period. All patients will be asked and this will enable us to compare the rate of genital recurrence in those patients with HSV-2 meningitis with the other groups of meningitis and controls. A separate questionnaire will be sent to record this to be returned anonymously with the other questionnaires.

6.4 Other Assessments

6.4.1 Meningitest

We will prospectively evaluate the 'meningitest'(22). This is a screening tool to improve the empirical diagnosis of viral or bacterial meningitis using initial blood and CSF parameters. This has previously been piloted retrospectively by members of our group(16).

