1 PROTOCOL SUMMARY

Title: UK Meningitis Study: Epidemiology and outcomes in meningitis in the UK – A prospective, observational, cohort study.

Population: A study looking at adults admitted to hospitals in the UK with suspected meningitis.

Inclusion Criteria

- a. 16 years or over
- b. Suspected Meningitis AND either
 - i) Have had or are going to have a lumbar puncture
OR
 - ii) If Lumbar puncture is contraindicated: the clinician has a strong suspicion of meningitis AND positive blood culture for bacterial pathogen consistent with meningitis OR radiology consistent with meningitis AND being treated as meningitis.

Exclusion Criteria

1. Patients with indwelling ventricular devices (EVD, VP shunts etc...) or iatrogenic meningitis
2. Patients in whom a lumbar puncture is contraindicated (except see b(ii) above)

Number of Sites: 35-45

Study Duration: 2 years extended to 5 years

Objectives:

[figure not shown]
Primary:

- To determine the prevalence of viral meningitis in adults hospitalised with suspected meningitis and how much of viral meningitis is attributable to herpes viruses, and other viruses.

Secondary:

- To examine the clinical and laboratory features, time to symptom resolution, neurological complications, neuropsychological sequelae, and recurrences in viral meningitis
- To compare these features and outcomes with those in bacterial meningitis and non-meningitic controls
- To prospectively evaluate the *Meningitest* – an algorithm for predicting viral or bacterial aetiology in meningitis
- To determine the number of people with aseptic meningitis being offered an HIV test and the proportion of these that are positive.
- To determine and describe the causes of aseptic meningitis in our region.
- To determine the costs to the NHS and to the patients.
- To determine the impact on the patient's quality of life.
- To evaluate the use of certain outcome measures in viral meningitis (HIT, ABNAS).
- To use these epidemiological and disease burden data to design a phase III study of aciclovir / valaciclovir in herpes meningitis.
- To evaluate new genomic and proteomic approaches in the diagnosis of meningitis.
- To evaluate new diagnostic techniques and methods
- To identify themes and barriers amongst clinicians and laboratory staff that may be associated with implementing new diagnostic tests for meningitis.

Schematic of Study Design

1.1 Substantial Amendment 17

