5 ENROLMENT

5.1 Screening

Screening criteria

- a) Over 16 years of age
- b) Suspected meningitis

Patients will be screened from participating hospitals when they have suspected meningitis (see definitions).

They will be allocated a screening number (including the site number) e.g. 01001 for site number 01, screening number 001.

They can be considered for inclusion in the study either by the admitting clinical teams (on clinical suspicion of meningitis), or by the diagnostic microbiology services (when they receive a CSF sample for analysis).

E.g.

Screening point 1:

A clinician identifies a patient that meets the inclusion criteria.

Screening point 2:

A laboratory identifies a CSF sample that is received in the microbiology department. The patient can then be screened for eligibility with regard to the inclusion criteria and clinically suspected meningitis.

Enrolment should occur within the same admission as the above tests are done.

A screening register or log will be required at each site and reasons for non-inclusion will be listed in the screening log. Screening log will be kept at site and at coordinating centre.

Definitions

SUSPECTED MENINGITIS

Illness for 3 weeks or less with:

Headache and one or both of:

- neck stiffness
- photophobia

*except for those with very sudden onset severe headache (defined as no pain to maximal pain within one minute).

OR

Other patients with symptoms in whom the clinician feels a lumbar puncture is needed to diagnose/exclude meningitis

MENINGISM

Headache with neck stiffness and/or photophobia

CSF ≤ 4 leukocytes per ml of CSF**.

(NB some of these patients may have positive microbiology/virology)

ASEPTIC MENINGITIS

Suspected Meningitis (as above), AND

Negative Cerebrospinal fluid (CSF) microscopy and culture for bacteria (or negative PCR for bacteria if on antibiotics prior to CSF sampling), AND

CSF white cell count of 5-1000 leukocytes per ml of CSF** (with a lymphocyte predominance unless total leucocyte count < 20)

and a CSF / Plasma glucose ratio of $> 40\%$ (if paired glucose taken).

WITH NO IMPAIRMENT OF CONSCIOUSNESS

(NB this group may be further subdivided into infective and non infective causes. If there are significant numbers of migraine in this group then they may also be separated out for purposes of analyses.)

PROVEN VIRAL MENINGITIS

Suspected meningitis, AND

CSF white cell count of >4 leukocytes per ml of CSF**

Positive CSF PCR for viral pathogen (or intrathecal antibody).

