6 ASSESSMENTS AND PROCEDURES

6.1 Baseline Tests

All patients will be asked if they have ever had a history of mouth or genital ulcers (if not already documented in the notes). And if they currently have any ulceration.

Opening Pressure will be recorded if LP is done in the lateral position.

CSF will be sent for

- Microscopy and Culture
- Protein
- Glucose

Further investigations:

Patients with **Aseptic Meningitis**

- Viral PCR - HSV 1 and 2
VZV
Enteroviruses
Parechoviruses (if routinely done by the treating centre).
Any other PCR that is deemed clinically appropriate in discussion with the clinical virologist/microbiologist (e.g. CMV, EBV in immunocompromised patients)
- HIV serology if no cause found
- Other investigations at the discretion of the responsible physician.

The viral CSF panel is what is regarded as 'good practice' amongst infection specialists and it has been shown that diagnosing viral meningitis reduces length of antibiotics and length of hospital stay and in turn brings a large cost saving.(15)

Patients with **Suspected Bacterial Meningitis**

- Meningococcal and Pneumococcal PCR on CSF (with consideration of 16S PCR if culture and meningo/pneumo PCR are negative – in discussion with local microbiologist).
 - PCR may be done routinely or only if culture negative depending on local practice.

If consented to all participants will have a small sample of CSF stored for future work on genomics/proteomics and other possible future studies. Participants will also be asked for permission to extract and sequence host and viral DNA from their specimens. (See section 1.1 for details of sub-studies.)

All participants will have **blood** tested for

- FBC, clotting, U and E's, LFTs, CRP, glucose ^(must be taken within 4 hours of LP)
- Blood Cultures
- Clotted sample to send for HSV type specific serology if HSV PCR on CSF positive
- Extra sample for gene expression, proteomic studies and other future studies. (see section 1.1)

Other Samples

In those with **Aseptic Meningitis**

- Throat swab and stool/rectal samples will be tested for enterovirus PCR
- Any oral or skin lesions present will be swabbed for HSV, VZV
- Any genital lesions will be swabbed for HSV PCR. *(if the PCR is negative for HSV in genital lesions the sample should then be referred (within the laboratory) for the CSF PCR panel as this is more sensitive, to exclude false negatives from the genital PCR.)*

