- Any vesicle fluid present will be tested for HSV, VZV, enterovirus and parechovirus (if available locally).

Again these samples are considered to be good practice and are reiterated in the Health Protection Agency's Standard Operating Procedure 48 (The investigation of viral encephalitis and meningitis.)

In those with proven **HSV meningitis**

- If self reported genital lesions present swab as above.
- HSV type specific serology at time of presentation
 - If type specific serology is IgG negative then further follow up type specific serology will be requested at 6 months to document seroconversion.(this can be done by the research nurse or fellow at the patient's home)
- If no genital lesions self reported participants will be asked to self swab for asymptomatic genital HSV infection as follows:
 - Men – swab penile skin and perianal area.
 - Women – swab vaginal, vulval and perianal area.

(Different swabs can be used for the different areas but all the swabs will be put into the same vial of transport medium.)

In order to find out if there is a link between genital HSV infection and undiagnosed aseptic meningitis we will also ask **all patients in the aseptic meningitis** group to take genital swabs, as above. We will advise these patients that if their swabs return positive we will contact them and suggest self referral to a local sexual health clinic. Currently the relationship between viral shedding and incidence of meningitis is unknown. We know from enterovirus infection of the CNS that we can find the virus outside of the CNS when it is not demonstrable in the CSF.

If a patient lacks capacity genital swabs will NOT be taken unless clinically indicated.

To facilitate in collection of the appropriate samples we will, where they are in place, use the pre – prepared lumbar puncture packs which are being rolled out in the northwest region for investigating patients with suspected meningitis. This follows previous work that showed patients were not having appropriate testing done.(16)

Those classed as having suspected bacterial meningitis can be treated with broad spectrum antibiotics in accordance with local policies and/or the British Infection Association Guidelines (17). Virological investigations will not be performed, but they will remain in the study for the comparative analyses of different pathogens, and disease burden, as described below.

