All these permutations mean potential delay in the final diagnosis, or no definitive diagnosis at all. With increasing centralisation of diagnostic laboratories it is likely that more CSF samples will travel further to be tested. Therefore it will be even more important to define what best practice should be with regard to microbiological diagnosis in cases of meningitis. One solution to these problems is for all CSF samples from patients with meningitis to have the same broadrange multiplex PCR covering all common central nervous system (CNS) pathogens. This would make the most of the available sample (because less sample is used in a multiplex test than multiple individual tests), eliminate the sample travelling to several laboratories thus reducing potential false negatives associated with frequent freeze/thawing. It would also counteract the fact that the requesting physician does not always request all of the appropriate tests at the outset.

Methods

Leftover CSF samples will be tested for common CNS pathogens using new commercially available multiplex kits, and also by singleplex PCR for a comprehensive array of pathogens, to evaluate the sensitivity of these kits.

Other molecular methods will also be used on leftover samples to establish if there are any novel pathogens contributing to meningitis in the UK.

MassTag PCR is a form of multiplex PCR that uses primers with tags of different molecular weights to identify the product. The MassTag PCR allows a rapid and sensitive diagnostic platform that can screen up to 30 bacterial, viral and fungal agents.

High throughput sequencing can be used to identify novel pathogens unidentified from conventional PCR techniques. In the few years since the development of high throughput sequencing the costs have decreased drastically and the speed increased.

These methods will be utilised with collaborators in the US and the UK.

Statistical analysis

Confirmed clinical cases (i.e. CSF white cell count >4 cells/ml), expected to be about 60% of all suspected cases, will be analysed by routine conventional testing and by variants of PCR testing as described above.

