7.3 Analysis Plan

Normally distributed data will be compared using Student's T test, and non-parametric tests, such as the Mann-Whitney U test, used for other data. Multiple logistic regression e.g. Cox regression, will be used to look for features predictive of particular pathogens. This will be adjusted for age and gender. Differences in median time to symptom resolution between groups will be analysed using two-sided actuarial (log-rank) methods, with a conventional 5% (type I error) significance level. The outcome analysis will also be adjusted for different research sites using multi-level modelling.

Assistance with analysis will be given by [name], Senior Lecturer in Epidemiology.

8 Safety Considerations

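### Routine virology is assigned by CSF class, so the Meningitest's specificity is liable to be overstated unless its reference diagnosis is made independently of CSF class

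*Protocol*

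**What the plan says.** The protocol summary (Section 1) lists prospective evaluation of the Meningitest, "an algorithm for predicting viral or bacterial aetiology in meningitis", as a secondary objective. Section 6.4.1 describes it: "This is a screening tool to improve the empirical diagnosis of viral or bacterial meningitis using initial blood and CSF parameters". The individual parameters are not listed and no reference diagnosis is named.

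Section 5.1 defines two CSF classes.
- **Aseptic:** 5 to 1000 leukocytes ("with a lymphocyte predominance unless total leucocyte count < 20") and, where a paired glucose was taken, a CSF/plasma ratio above 40%.
- **Purulent (suspected bacterial):** 20 to 1000 leukocytes with polymorphs predominating, or more than 1000 of any type, and a ratio below 40% where paired.

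Section 6.1 then assigns the work-up by class.
- The viral PCR panel stands under "Patients with Aseptic Meningitis".
- The suspected bacterial group is listed for "Meningococcal and Pneumococcal PCR on CSF (with consideration of 16S PCR if culture and meningo/pneumo PCR are negative".
- Of that second group the section says: "Virological investigations will not be performed, but they will remain in the study for the comparative analyses of different pathogens".

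The table in 6.2 repeats this split, and the footnote to the schedule in 6.7 ties the choice of PCR to cell count or clinical judgement.

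Under 5.1, proven viral meningitis requires a positive CSF viral PCR or intrathecal antibody. Proven bacterial meningitis requires a pathogen from blood or CSF by culture, nucleic acid detection or serology. Section 7.3 adds regression models that "will be used to look for features predictive of particular pathogens".

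**The concern.** A diagnostic rule is judged fairly when the chance of having one's true disease confirmed does not depend on what the rule looks at. Here it does. A viral case with a purulent CSF has no routine route to being proven viral, and it is the kind of viral case that a rule using CSF is likely to call bacterial. If only proven cases are analysed, these errors leave the denominator and the rule looks better than it is. This is differential verification.

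The problem lies in the work-up the protocol prescribes. A statistical analysis plan can name a reference standard, but it cannot recover virology that was never done.

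At stake is a named secondary objective. A viral-versus-bacterial rule that looks more specific than it is could be carried forward on false assurance. The 7.3 models share the problem where they contrast viral with bacterial disease using the CSF features that define the classes: cell count, cell type and glucose ratio.

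**Working it through.** The protocol gives no sensitivity, specificity, power or sample size for the Meningitest, so there is no stated figure to reproduce. The calculation below shows direction and range only. **Every rate in it is an assumption**; the documents supply none.

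**Notation.** A positive test means it calls the case bacterial.
- c_B, c_V: share of bacterial and of viral cases with a purulent CSF
- t_P, t_A: probability of a positive test given purulent and given aseptic CSF
- k: culture yield in bacterial cases
- p: share of culture-negative bacterial cases found by bacterial PCR
- a: share of aseptic-CSF bacterial cases that get bacterial PCR
- m: share of otherwise untested cases covered by PCR done regardless of class

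**Specificity**

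True = 1 − [c_V·t_P + (1 − c_V)·t_A]

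Apparent = 1 − [c_V·m·t_P + (1 − c_V)·t_A] / [c_V·m + (1 − c_V)]. The viral PCR yield cancels.

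With m = 0, apparent = 1 − t_A and the overstatement is c_V·(t_P − t_A).

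Take t_P = 0.95 and t_A = 0.10:
- c_V = 0.10: true 1 − (0.095 + 0.090) = 81.5%; apparent 90.0%; overstated by 8.5 points.
- c_V = 0.20: true 1 − (0.190 + 0.080) = 73.0%; apparent 90.0%; overstated by 17 points.
- c_V = 0.20, m = 0.5: apparent 1 − (0.095 + 0.080)/(0.10 + 0.80) = 80.6%; overstated by 7.6 points.
- c_V = 0.20, m = 1: apparent 73.0%; no bias.
- t_P = t_A: no bias, because the test is then unrelated to CSF class within each aetiology.

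**Sensitivity**

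True = c_B·t_P + (1 − c_B)·t_A. With c_B = 0.85 this is 0.8075 + 0.0150 = 82.25%.

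The proportion proven is v_P = k + (1 − k)·p in purulent CSF and v_A = k + (1 − k)·p·a in aseptic CSF (m = 0). Apparent sensitivity is the average of t_P and t_A with weights c_B·v_P and (1 − c_B)·v_A.

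Take k = 0.40 and p = 0.60, so v_P = 0.76 and the purulent weight is 0.85 × 0.76 = 0.646:

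| a | v_A | Aseptic weight | Apparent sensitivity | Overstated by |
|---|---|---|---|---|
| 0 | 0.40 | 0.060 | 0.6197/0.706 = 87.8% | 5.5 points |
| 0.5 | 0.58 | 0.087 | 0.6224/0.733 = 84.9% | 2.7 points |
| 1 | 0.76 | 0.114 | 0.6251/0.760 = 82.25% | 0 |

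A harsher set (c_B = 0.70, k = 0.30, p = 0.70, a = 0) gives true 69.5%, apparent 83.1%, overstated by 13.6 points.

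Specificity stays at 90.0% against a true 73.0% in all three rows if c_V = 0.20 and m = 0. More bacterial PCR does nothing for the missing viral cases.

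**The case against.** The case on the other side has substance.

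- **The overlap is partly inferred.** A reader might infer that the Meningitest uses the very values that define the CSF classes. Section 6.4.1 says only blood and CSF parameters. Some dependence on CSF is stated; its degree is not, and the blood parameters dilute it. This stands.
- **No reference is named.** That choice may belong to the analysis plan, so the bias is conditional on using the proven-case definitions. A reader might also infer that the aseptic/purulent class is to serve as the truth. That would be circular, but the protocol never proposes it.
- **Bacterial PCR is not confined to purulent CSF.** The aseptic definition in 5.1 calls for negative bacterial PCR when antibiotics preceded CSF sampling, and CSF and blood cultures are planned for everyone. A firm claim that sensitivity is overstated is therefore not supported. These provisions do not touch specificity.
- **Not every atypical viral case falls in the excluded class.** A polymorph-predominant CSF with a paired glucose ratio above 40% does not meet the purulent definition. It does not meet the aseptic one either if the count is 20 or more, so neither investigation list clearly covers it. This narrows the affected group without removing it.
- **Not every CSF feature is affected.** Protein and opening pressure define neither class. Comparisons between viruses within the aseptic group share one panel and are not touched by this argument.
- **The remedy is largely in hand.** Section 6.9.2 states: "Leftover CSF samples will be tested for common CNS pathogens using new commercially available multiplex kits", together with singleplex PCR, for confirmed cases (more than 4 cells) whatever their profile. This is correct, but nothing links that work to 6.4.1 or 7.3.

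**Conclusion.** The concern holds in a limited form. Because virology is withheld from the suspected bacterial class and proven viral disease needs a positive virological result, the Meningitest's apparent specificity is liable to be too high if the protocol's proven cases are the reference. The same applies to viral-versus-bacterial models in 7.3 that use cell count, cell type or glucose ratio. Any sensitivity bias may be small or nil.

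The size cannot be known from the documents. The range of 8.5 to 17 points for specificity assumes that 10% to 20% of viral cases have a purulent CSF, that the test follows CSF class strongly but not perfectly, and that no PCR is done across classes. A reader might expect observed specificity close to 100%. That follows only if the test is assumed to reproduce CSF class exactly (t_P = 1, t_A = 0), in which case it is 100% by construction. Nothing in the protocol supports that assumption.

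This is a point worth correcting on a secondary objective; the primary objective is not at issue here.

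**What to change.** In 6.4.1 and 7.3:
1. State that the reference diagnosis is the pathogen found by CSF or blood culture plus the PCR planned in 6.9.2 on leftover CSF of confirmed cases, whatever their CSF profile.
2. Let singleplex PCR anchor that reference, with multiplex results as support, since 6.9.2 is itself evaluating the multiplex kits.
3. State that the aseptic/purulent class is not to be used as the truth.
4. Report the result based on the routine work-up alongside.
5. Compare patients with and without leftover CSF, because 6.9.2 itself notes that samples are often used up.

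This needs wording and one linkage of results already planned, with no new procedure and no change to care. The price is fewer evaluable patients, a reference that partly rests on kits under evaluation, and probably less flattering accuracy figures.

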6.4.2 Headache Impact Test (HIT)™

This will be used to assess the impact headaches have on a person's ability to function on the job, at home, at school and in social situations. This tool which is particularly suitable for assessing the long term morbidity, has been developed for migraine and chronic headache (<http://www.headachetest.com/>) (23). We will compare between the groups of patients with viral meningitis and other types of meningitis. If there is a significant group of patients with migraine then they will also be used as a comparator group. Post LP headache will be defined as either a) new onset headache or b) worsening of headache following lumbar puncture which is worse on being vertical and eased on lying down with no other cause found.

6.4.3 Quality of Life and Health Economics

6.4.3.1 Quality Of Life Assessment - SF36

Quality of Life will be assessed using a generic health status measure, the SF36 (24) and the EQ-5D(25). The SF-36 assesses health status across eight domains: physical and social function, roles physical and emotional, mental health, energy/vitality, pain and general health; it also includes a 'transition' question (assessing perceived change in health status over time). It is a self-completion questionnaire, that been validated for use across a range of conditions of ill-health (24); and UK normative data are available, and takes between 5 and 10 minutes to complete. In addition, in order to obtain utilities for the economic analysis the EQ-5D will be used. The EQ-5D is a standardised non-specific multidimensional self completed questionnaire that describes and values health states, expressing results in a single index value of quality of life. It is based on a descriptive classification of five dimensions: mobility, self-care, usual activities, pain/discomfort and anxiety/depression. Each dimension has three levels 'no problem', 'some problem' and 'extreme problem'; death and unconscious health states are added creating a total of 245 health states for the evaluation. We will also include a single-item global quality of life question.

